7.3 Serious Adverse Event Reporting

7.3.1 Sponsor Notification

Any serious adverse event or event of clinical interest must be reported to the Central Office within 24 hours of the Investigator at the site learning of the event by a completed SAE form. The adverse event must be completely described in the case report form.

The Central Office will provide expedited reports of on-study SAEs to Health Canada and Merck for those events which meet regulatory requirements for expedited reporting, i.e. events which are BOTH serious AND unexpected (as determined by reference to the Investigator Brochure), AND which are thought to be related to protocol treatment (or for which a causal relationship with protocol treatment cannot be ruled out).

All adverse signs and symptoms which occur during or following the course of drug administration must be reported in detail on the subject’s case report form. This description is to include the nature of the sign or symptom, time of onset in relation to drug application, duration, severity, and possible relationship to drug, required therapy, and outcome. The subject should be followed until the adverse reaction is resolved, or until in the opinion of the Principal Investigator, reversal of the reaction is not likely to occur.

7.3.2 SAE Follow-up

Follow-up SAE reports is subject to the same timelines as the initial report, and is sent to the same parties to whom the original Serious Adverse Event Form was sent. A new serious adverse event form is completed for the follow-up, stating that this is a follow-up to the previously reported serious adverse event and giving the date of the original report. Each re-occurrence, complication or progression of the

original event should be reported as a follow-up to that event. The follow-up information should describe whether the event has resolved or continues, if and how it was treated, and whether the subject continued or discontinued study participation.

The Sponsor-Investigator and Institution will assist Merck in investigating any SAE and will provide any follow-up information reasonably requested by Merck.

7.3.3 REB Notification of SAEs

Investigators must notify their Research Ethics Boards (according to their local REB policies) and file the report in their study files. Documentation as outlined below must be maintained for reportable SAEs. Documentation that serious adverse events (SAEs) have been reported to REB must be forwarded to the Central Office and kept on file at the Centre. Documentation can be any of the following:

- letter or email from the REB acknowledging receipt
- stamp from the REB, signed and dated by REB chair, acknowledging receipt
- letter or email demonstrating the SAE was sent to the REB

7.3.4 Health Canada SAE Reporting

All serious, unexpected adverse drug reactions must also be reported by the Central Office to Health Canada within 15 days if the reaction is neither fatal nor life threatening, and within 7 days if the reaction is fatal or life threatening.

As Princess Margaret Cancer Centre is the sponsor delegate of this study in Canada, the Central Office of this study will be responsible for reporting all serious unexpected adverse events to Health Canada.

7.3.5 SAE Reporting to Merck

To ensure subject safety, each serious adverse event or hepatic event of clinical interest must also be reported by the Central Office to Merck Global Safety (in English) within 24 hours of learning of its occurrence, even if it is not felt to be treatment-related (Attn: Worldwide Product Safety; [contact]). Follow-up information about a previously reported serious adverse event must also be reported within 24 hours of the Investigator-sponsor receiving it. The SAE Report Form must indicate the relationship to study treatment and be signed by the investigator. All reports of overdose with and without an adverse event must be reported within 24 hours to the Central Office, and within 2 working days by the Central Office to Merck Global Safety.

7.4 Routine Adverse Event Reporting

For abnormal laboratory values, it is the responsibility of the Principal Investigator to assess the clinical significance of each abnormality. Only abnormal laboratory values that can be assessed for grade using CTCAE v4.0 will be documented. The Investigator will determine whether abnormal laboratory values are considered clinically significant and represent AEs based on their medical judgment.

Data on all adverse experiences/toxicities regardless of seriousness must be collected for documentation purposes only.

Clinical Laboratory Abnormalities:

All abnormal laboratory values should be captured on source documentation and assessed for clinical significance by the Investigator at the site. Only abnormal laboratory values deemed clinically significant should be listed as AEs in the CRFs. All clinically significant abnormal laboratory results will be followed up until the related AE resolves, returns to < grade 1 or baseline value in the follow-up period. Clinically significant laboratory abnormalities will be dictated in the clinic notes. Additionally, laboratory abnormalities resulting in an intervention are considered to be clinically significant.

7.5 Documentation of Adverse Events

All AEs must be captured in the source documents, as well as reported in *electronic document capture (EDC) system*. AEs reported using SAE forms must also be reported in *EDC system*.

All serious and non-serious AEs occurring from the start of study medication administration to the end of study drug administration visit must be recorded as AEs on the CRF. The Investigator should review all documentation (e.g., hospital progress notes, laboratory, or diagnostic reports) relative to the event being reported.

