5. TREATMENT PLAN

5.1 Agent Administration

Treatment will be administered on an outpatient basis. Appropriate dose delays and management of adverse events are described in Section 6. No investigational or commercial agents or therapies other than those described below may be administered with the intent to treat the subject's malignancy.

Regimen Description			
Agent	Dose	Route	Schedule
Pembrolizumab	200 mg	IV over 30 minutes	Every 3 weeks
SBRT administered to dominant hepatic HCC			Starting day 2 of cycle 1 pembrolizumab, given in 5 fractions over 5-15 days

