5.1.2.1 Prescription Dose

Absorbed dose: 27.5 Gy - 50 Gy in 5 fractions. The prescription dose may be 50 Gy, 45 Gy, 40 Gy, 35 Gy, 30 Gy or 27.5 Gy in 5 fractions, based on normal tissue constraints. The dose to multiple PTVs may be different. The goal is to use the highest allowable prescription dose to the primary target, while respecting normal tissue constraints. The minimal planned prescription dose to PTVs is 27.5 Gy. Given the novelty of this combination, and the potential for overlapping hepatic toxicity, the first 10 patients will have to meet all the following additional liver dosimetric constraints:

- 1) Mean liver (minus gross HCC tumor volume) dose < 15 Gy in 5 fractions.
- 2) $D_{800cc} \leq 18$ Gy in 5 fractions
- 3) Biologically corrected normal tissue complication probability (NTCP) $< 0.5\%$

If 2 or fewer patients of the first 10 patients experience grade 3 hepatic toxicity at this dose, we will increase to standard dosing. If 3 or more patients experience grade 3 toxicity, or if any patients experience grade 4/5 toxicity in first 3 months following SBRT, these dose constraints will be maintained for all patients on study and modification of all SBRT dose constraints will be considered.

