5.4 Duration of Follow Up

Subjects removed from therapy for reasons other than progressive disease/iCPD will be followed at intervals of 90 days (± 14 days) for disease status until progression or initiation of alternative therapy. Follow-up visits can occur remotely via telephone, Ontario Telemedicine Network (OTN), or other appropriate virtual communication if it is in patient's best interest, at the discretion of the Investigator. Subjects who withdraw for refusal will no longer be followed. All subjects will be followed for survival every 90 days (± 14 days) for survival status until death via telephone, in-person visit, or via medical records.

Table 6: Follow-up Guideline

Reason Subjects Removed from study	Follow-Up Period			
	Off Treatment Visit: 4 weeks ± 7 days from the End of Study Drug Administration	Progression Follow-Up: every 3 months ± 14 days after the Off Treatment Visit *	Adverse Event Follow-Up: until resolution or stabilization of adverse event(s)	Survival Follow-Up: every 3 months ± 14 days after the Off Treatment Visit
Objective Disease Progression	X		X	X
Clinical Progression/ Symptomatic Deterioration	X	X	X	X
Adverse Events or clinically significant lab value	X	X	X (weekly FU for 4-weeks, then monthly)	X
All other subjects	X	X	X	X

* Confirmed disease progression (iCPD) is defined according to iRECIST.

** See section 7.6 for Adverse Event Follow-Up details

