6. DOSING DELAYS/MODIFICATIONS AND TOXICITY MANAGEMENT

6.1 Pembrolizumab Dose Modification

Adverse events (both non-serious and serious) associated with pembrolizumab exposure may represent an immunologic etiology. These adverse events may occur shortly after the first dose or several months after the last dose of treatment. Pembrolizumab must be withheld for drug-related toxicities and severe or life-threatening AEs as per Table 7 below. See Section 5.2 for supportive care guidelines, including use of corticosteroids.

Table 7: Dose Modification and Toxicity Management Guidelines for Immune-related AEs Associated with Pembrolizumab

General instructions:

1. Corticosteroid taper should be initiated upon AE improving to Grade 1 or less and continue to taper over at least 4 weeks.
2. For situations where pembrolizumab has been withheld, pembrolizumab can be resumed after AE has been reduced to Grade 1 or 0 and corticosteroid has been tapered. Pembrolizumab should be permanently discontinued if AE does not resolve within 12 weeks of last dose or corticosteroids cannot be reduced to ≤ 10 mg prednisone or equivalent per day within 12 weeks.
3. For severe and life-threatening irAEs, IV corticosteroid should be initiated first followed by oral steroid. Other immunosuppressive treatment should be initiated if irAEs cannot be controlled by corticosteroids.

Immune-related AEs	Toxicity grade or conditions (CTCAEv4.0)	Action taken to pembrolizumab	irAE management with corticosteroid and/or other therapies	Monitor and follow-up
Pneumonitis	Grade 2	Withhold	• Administer corticosteroids (initial dose of 1-2 mg/kg prednisone or equivalent) followed by taper	
• Monitor participants for signs and symptoms of pneumonitis• Evaluate participants with suspected pneumonitis with radiographic imaging and initiate corticosteroid treatment• Add prophylactic antibiotics for opportunistic infections
	Grade 3 or 4, or recurrent Grade 2	Permanently discontinue		
Diarrhea / Colitis	Grade 2 or 3	Withhold	• Administer corticosteroids (initial dose of 1-2 mg/kg prednisone	
• Monitor participants for signs and symptoms of enterocolitis (ie, diarrhea, abdominal pain, blood or mucus in stool with or without

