7.1.1.2 Expected Adverse Events for SBRT

Very likely (80-90%)

- Fatigue (which generally resolves after radiation therapy is completed)
- Skin irritation, redness, itchiness, discomfort
- Temporary changes in blood work, without symptoms

Less likely (30%)

- Nausea, vomiting (during therapy) – more common if stomach or GI tract irradiated
- Diarrhea or sensitivity to food – more common if GI tract irradiated
- Gastritis, esophagitis, duodenitis, colitis – more common if relevant portion of the GI tract is irradiated
- Gastric, esophagus, small bowel or large bowel irritation/ulceration, bleeding, fistula, obstruction or changes in motility following therapy (may require medications or surgery) (<10% permanent changes)
- Chest wall pain, rib fracture (< 10%)

Less likely, but serious (<1-25%)

- Radiation-induced liver disease (RILD) (<5%). Classic RILD is a clinical diagnosis of anicteric ascites, hepatomegaly and elevation of ALP relative to other transaminases that may occur 2 weeks to 3 months following radiation to the liver.
- Non-classic RILD includes elevation of liver enzymes and/or any decline in liver function within 12 weeks from start of therapy (~25%). RILD can lead to liver failure that could lead to death. There is an increased risk of liver toxicity in patients with large tumors and in patients with pre-existing liver disease.
- Permanent thrombocytopenia (<1%); this may lead to bleeding
- Kidney injury (<1%); this may lead to changes on imaging and more rarely the need for medication.

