7.6 Follow-Up of AEs and SAEs

All SAEs and AEs should be followed until 4 weeks after the last dosing of study drug/biologic or until they are resolved (return to normal or baseline values), stabilized, improve to < Grade 2, or the subject is lost to follow-up and cannot be contacted. Additional investigations (e.g., laboratory tests, diagnostic procedures, or consultation with other healthcare professionals) may be required to completely investigate the nature and/or causality of an AE or SAE. If the subject dies during the study or within 4 weeks following the last dose of study medication, any postmortem findings (including histopathology) should be provided to the Sponsor.

After the Off Treatment Visit, only AEs considered related to study drug are to be followed until resolution (return to normal or baseline values), stabilized, improve to < Grade 2, patient starts another treatment, or the subject is lost to follow-up and cannot be contacted.

CRF data should be updated with any new information as appropriate.

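### Routine AE recording and scheduled liver tests end with pembrolizumab, so part of the 3 months after SBRT can go unobserved in patients with about four or fewer doses

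*Combined protocol and SAP*

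**What the plan says.** **When recording ends.** Section 7.5: "All serious and non-serious AEs occurring from the start of study medication administration to the end of study drug administration visit must be recorded" on the CRF. Table 6 in 5.4 fixes the closing visit by the drug: "Off Treatment Visit: 4 weeks ± 7 days from the End of Study Drug Administration". Section 7.6 then narrows follow-up: "After the Off Treatment Visit, only AEs considered related to study drug are to be followed until resolution" or one of the other listed end points, including the start of another treatment. SBRT is not named there.

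**What is scheduled later.** In the Section 10 calendar, the Survival Follow-Up column carries survival status. Footnote i adds three-monthly tumor assessment for patients who stopped without radiological progression. No chemistry, INR or Child-Pugh score is visible after the Off Treatment Visit.

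**When toxicity is expected.** Section 7.1.1.2 describes classic radiation-induced liver disease as an event "that may occur 2 weeks to 3 months following radiation to the liver", and places the non-classic form within 12 weeks of starting therapy in about 25%. Section 6.1 says of immune-related events: "These adverse events may occur shortly after the first dose or several months after the last dose of treatment".

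**What depends on it.** Section 5.1.2.1: "If 2 or fewer patients of the first 10 patients experience grade 3 hepatic toxicity at this dose, we will increase to standard dosing". The added constraints stay if three or more patients have grade 3 toxicity, or "if any patients experience grade 4/5 toxicity in first 3 months following SBRT".

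**The concern.** The clock for routine AE recording starts and stops with pembrolizumab, whereas the liver toxicity of most interest runs from SBRT. For a patient who stays on drug the two periods overlap and nothing is lost. For a patient who stops early, recording and scheduled testing can close well before three months after radiation.

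The events exposed are new, non-serious and mainly laboratory-based: a grade 3 rise in ALT, AST or bilirubin with no symptoms that bring the patient in. These are the kind of event the grade 3 count in 5.1.2.1 relies on. A missed event can only lower that count, so the error runs one way: toward relaxing the added liver constraints and toward a more favorable toxicity table for a combination that the background section says lacks prospective data in HCC.

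**Working it through.** **Step 1. Closing visit.** From 5.4, 4 weeks ± 7 days = 28 ± 7 = 21 to 35 days after the last dose. Cycles are 21 days (Section 10), so dose k is given on day 1 + 21(k − 1). I read the visit named in 7.5 as the Off Treatment Visit. The term is not defined; if it means the last dosing visit, recording closes 21-35 days earlier.

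**Step 2. Three months after SBRT.** SBRT starts on day 2, "given in 5 fractions over 5-15 days" (5.1), so the last fraction falls between day 6 and day 16. Taking three months as 91 days (my assumption): 6 + 91 = day 97 and 16 + 91 = day 107.

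**Step 3. Gap = (last fraction + 91) − closing visit.**

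| Doses | Last dose (day) | Closing visit (day) | Unobserved days before 3 months after SBRT |
|---|---|---|---|
| 1 | 1 | 22-36 | 61-85 |
| 2 | 22 | 43-57 | 40-64 |
| 3 | 43 | 64-78 | 19-43 |
| 4 | 64 | 85-99 | 22 short to 2 beyond |
| 5 | 85 | 106-120 | at most 1 |
| 6 | 106 | 127-141 | none |

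For one dose, for example: 97 − 36 = 61 and 107 − 22 = 85. The gap is certain after one to three doses, usual after four and negligible from five. Against the shorter 12-week period for non-classic disease (day 2 + 84 = day 86), the nominal four-dose visit on day 92 is late enough; visits after one to three doses are not.

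**Step 4. Effect on the first-10 count.** The documents give neither a grade 3 hepatic rate nor the share of events that come late, so both are assumed. With true rate p and share m of events missed across the ten patients, the recorded rate is q = p(1 − m), and

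P(3 or more of 10) = 1 − Σ C(10,x) q^x (1 − q)^(10−x), summed over x = 0 to 2.

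For p = 0.30, m = 0: 1 − (0.028 + 0.121 + 0.233) = 0.617. For m = 0.30, q = 0.21: 1 − (0.095 + 0.252 + 0.301) = 0.353 (computed from unrounded terms).

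| True rate p | m = 0 | m = 10% | m = 30% | m = 50% |
|---|---|---|---|---|
| 10% | 0.070 | 0.054 | 0.028 | 0.012 |
| 20% | 0.322 | 0.263 | 0.155 | 0.070 |
| 25% | 0.474 | 0.398 | 0.248 | 0.120 |
| 30% | 0.617 | 0.534 | 0.353 | 0.180 |

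**Step 5. The AE end dates side by side.**

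- 7.5: the visit closing study drug administration.
- 7.6: after the Off Treatment Visit, follow-up only of events related to study drug.
- 7.2: serious events until four weeks after study participation ends, and later if pembrolizumab or SBRT is suspected.
- 7.3.1: signs and symptoms arising while drug is given or afterwards go on the case report form, with no end date.

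These do not describe one recording period.

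**The case against.** The strongest reply is that much is still captured. Section 7.2 counts from the end of study participation, and 5.5 defines removal from study by death, withdrawal of consent, loss to follow-up or termination, not by the last dose. Serious events therefore remain reportable through follow-up. Section 7.3.1 requires serious events and events of clinical interest to be reported within 24 hours of the site learning of them, and 6.2 defines hepatic events of clinical interest to include ALT, AST and bilirubin rises. Table 6 gives patients removed for an AE or laboratory value weekly and then monthly follow-up, and survival is followed until death. All of this stands. A reader might infer that early stoppers leave observation; the documents do not support that.

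A reader might also infer that early stoppers leave mainly for liver problems and so lose the events that matter most. No source supports it, and a patient who stopped for a recorded grade 3 liver event is already in the count.

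The exposed group may be small. The first on-treatment scan is at 12 weeks and iRECIST progression needs confirmation, so radiographic progression alone would rarely end treatment after one to three doses. Clinical progression and other reasons remain, and a patient taken off at the first scan may have had only four doses.

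The three-month phrase clearly belongs only to the grade 4/5 clause, and the roughly 30% decline at three months in 2.2.2 concerns Child-Pugh score after six-fraction SBRT, not grade 3 toxicity. Neither can be used to claim a known loss of grade 3 events.

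What survives is detection. A reporting duty that begins when the site learns of an event does not help if no test is scheduled to reveal it, and 7.5 does not require a new non-serious event after the closing visit to be recorded, whatever 7.3.1 says.

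**Conclusion.** The point holds in a limited form and should be fixed. For patients with one to three doses, and usually four, a new non-serious grade 3 hepatic laboratory event can fall after routine recording and visible liver testing have ended but within three months of SBRT. The bias in the first-10 count and in the toxicity summary can only be downward.

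Its size cannot be established from the documents. Over assumed true rates of 10-30% with 30-50% of events missed, the chance of recording three or more in ten falls, for example, from 0.62 to 0.35 (30% rate, 30% missed) or from 0.07 to 0.01 (10% rate, 50% missed). With 10% missed at a 30% rate the fall is only to 0.53. These figures apply the missed share to all ten patients and are illustrations, not estimates.

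Two further assumptions matter: that the visit in 7.5 is the Off Treatment Visit, and that the calendar has been read correctly. Its columns are misaligned in the available copy, so which tests are done at the Off Treatment Visit itself cannot be confirmed, and no claim is made about that.

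**What to change.** 1. In 7.5, 7.6 and the Section 10 calendar, record all AEs and schedule the existing liver panel (chemistry, INR, Child-Pugh) until the later of the Off Treatment Visit and three months after the last SBRT fraction, for every patient who received SBRT and remains in follow-up.
2. In 7.6, replace the reference to study drug with pembrolizumab or SBRT, in line with 7.2.
3. Reconcile the AE end points in 7.2, 7.3.1, 7.5 and 7.6, and define the closing visit named in 7.5.
4. Reconcile the grade 3 and grade 4/5 clauses of 5.1.2.1 with each other and with the period over which hepatic toxicity is actually observed. How that rule should operate is for the investigators.

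The cost is a short amendment, one or two extra routine blood draws and AE checks in patients who stop early, and possibly a slightly higher reported toxicity rate. Patients who withdraw by refusal are no longer followed under 5.4, so the change will not reach them.

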7.6 Follow-Up of AEs and SAEs

All SAEs and AEs should be followed until 4 weeks after the last dosing of study drug/biologic or until they are resolved (return to normal or baseline values), stabilized, improve to < Grade 2, or the subject is lost to follow-up and cannot be contacted. Additional investigations (e.g., laboratory tests, diagnostic procedures, or consultation with other healthcare professionals) may be required to completely investigate the nature and/or causality of an AE or SAE. If the subject dies during the study or within 4 weeks following the last dose of study medication, any postmortem findings (including histopathology) should be provided to the Sponsor.

After the Off Treatment Visit, only AEs considered related to study drug are to be followed until resolution (return to normal or baseline values), stabilized, improve to < Grade 2, patient starts another treatment, or the subject is lost to follow-up and cannot be contacted.

CRF data should be updated with any new information as appropriate.

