Protocol ID: PEMRAD
Version Date: 09-Sep-2021

Protocol ID: PEMRAD

Protocol Version/ Date: Initial / 11Apr2017
Amendment #1 / 01-May-2018
Amendment #2 / 06-Nov-2019
Amendment #3 / 20-Nov-2020
Amendment #4 / 09-Sep-2021

TITLE: Pembrolizumab and Stereotactic Radiotherapy Combined in Subjects with Advanced Hepatocellular Carcinoma – A Phase II Study (PEMRAD)

Coordinating Center: Princess Margaret Cancer Centre
[name]
[name]
Canada

Sponsor-Investigator: **[name]**
Princess Margaret Cancer Centre
[name]
[name]
Canada
[contact]
[contact]
Email: [contact]

Radiation Oncology Lead: **[name]**
Princess Margaret Cancer Centre
[name]
[name]
Canada
[contact]
Email: [contact]

Hepatology Lead: **[name]**
Princess Margaret Cancer Centre
[name]
[name]
Canada
Email: [contact]

Participating Institutions: Princess Margaret Cancer Centre
[name]
[name]
Canada

Statistician:

[figure not shown]
[name]
Department of Biostatistics
Princess Margaret Cancer Centre
[name]
[name]
[contact] [name]
[contact]
[contact]

Central Office Coordinator:

[name]
Drug Development Program
Princess Margaret Cancer Centre
[name]
[name]
[contact] [name]
[contact]
[contact]

Investigational Agent: Pembrolizumab

SCHEMA

*SBRT will be given daily or every 2nd day on weekdays, and therefore cycle days may not correspond. Schema is for illustration purposes only. All treatment dates +/- 1 day.

SYNOPSIS

Title of study: 
Pembrolizumab and Stereotactic Radiotherapy Combined in Subjects with Advanced Hepatocellular Carcinoma – A Phase II Study (PEMRAD)

Objectives: 
Primary:
 
• To assess the efficacy of combined SBRT and pembrolizumab in subjects with advanced hepatocellular carcinoma (HCC), by measurement of overall response rate (ORR). 
Secondary:
 
• To assess response rate outside irradiated volumes (abscopal effect)• Analyze response kinetics• Determine progression-free and overall survival• Assess safety of combined SBRT and pembrolizumab. 
Exploratory:
 
• To explore predictors of response to combined SBRT and pembrolizumab in HCC, including molecular and imaging biomarkers associated with response outside irradiated volumes.

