- Important medical events that may not result in death, be life-threatening, or require hospitalization may be considered serious when, based upon appropriate medical judgment, they may jeopardize the subject and may require medical or surgical intervention to prevent one of the outcomes listed in this definition (Examples include allergic bronchospasm requiring intensive treatment in an emergency room or at home, blood dyscrasias or convulsions that do not result in hospitalization or the development of drug dependency or drug abuse).

Any malignancy possibly related to cancer treatment (including AML/MDS) should be reported as an SAE. A second malignancy is one unrelated to the treatment of a prior malignancy (and is NOT a metastasis from the initial malignancy).

Events not considered to be serious adverse events are:

- hospitalizations for the routine treatment or monitoring of the studied indication, not associated with any deterioration in condition,
- treatment, which was elective or pre-planned, for a pre-existing condition that is unrelated to the indication under study and did not worsen,
- admission to a hospital or other institution for general care, not associated with any deterioration in condition, or
- treatment on an emergency, outpatient basis for an event not fulfilling any of the definitions of serious given above and not resulting in hospital admission.

Any SAE occurring after the subject has provided informed consent and until 4 weeks after the subject has stopped study participation must be reported. This includes the phase in which the study protocol interferes with the standard medical treatment given to a subject (e.g. treatment withdrawal during screening phase, change in treatment to a fixed dose of concomitant medication). Serious adverse events occurring more than 4 weeks after study discontinuation need only be reported if a relationship to pembrolizumab or SBRT is suspected.

Unexpected adverse treatment experience: Any adverse drug/biologic experience, the nature, frequency, or severity of which is not consistent with the product monograph, or not consistent with the risk information described above as a protocol-specific expected adverse event (see “Expected Adverse Events and Protocol-Specific Expedited Adverse Event Reporting Exclusions”, above).

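### Section 7.6 limits adverse event follow-up after the Off Treatment Visit to events related to study drug, in conflict with Table 6 and Section 7.2, so the later course of some SBRT-only events may go unrecorded

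*Combined protocol and SAP*

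**What the plan says.** Section 7.6 has two stages. Up to four weeks after the last dose, every adverse event is followed whatever its cause, unless it resolves, stabilises or falls below grade 2 sooner. After that the rule narrows: "After the Off Treatment Visit, only AEs considered related to study drug are to be followed until resolution". The section uses *study drug* in the language of dosing, and the cover page lists one agent: "Investigational Agent: Pembrolizumab".

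Other places are worded differently:

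- **Section 5.4, Table 6** ticks adverse event follow-up, to resolution or stabilisation, for every reason for removal and sets no attribution limit. Subjects removed for an adverse event or a clinically significant laboratory value are followed weekly for four weeks, then monthly. A footnote adds "See section 7.6 for Adverse Event Follow-Up details".
- **Section 7.2** attributes events to the study treatment as a whole. It says that serious events arising more than four weeks after study discontinuation "need only be reported if a relationship to pembrolizumab or SBRT is suspected".
- **Section 7.3.1** says "The subject should be followed until the adverse reaction is resolved", or until reversal is judged unlikely. Its context is signs and symptoms during or after drug administration.

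Table 6 places the Off Treatment Visit at "4 weeks ± 7 days from the End of Study Drug Administration".

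**The concern.** SBRT is half of the treatment under test, and Section 7.1.1.2 lists its expected harms: liver injury, bowel ulceration, chest wall pain and rib fracture among them. If the filter in 7.6 is applied as worded, a non-serious event judged due to SBRT alone and unresolved at the Off Treatment Visit has no stated follow-up. A pembrolizumab event in the same state does.

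Two uses of the data could be touched. Section 13.6.1 tabulates adverse events by type and grade, so an event that worsens after the visit could be entered at too low a grade. Section 5.1.2.1 uses hepatic toxicity in the first 10 patients, and names the first three months after SBRT, to decide whether the additional liver constraints stay in place. An early stopper among those 10 could have an open hepatic event that is not followed to the end of that period.

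The issue here is the attribution filter on events already recorded and still open. The period for recording new events, set in Section 7.5, is a separate matter.

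**Working it through.** The plan states no figure on this point, so there is none to reproduce. The check has two parts.

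**1. Which open events fall outside follow-up if 7.6 governs?**

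| Event open at the Off Treatment Visit | Provision | Still followed? |
|---|---|---|
| Related to pembrolizumab | 7.6 | Yes |
| Possibly related to both components | 7.6, with attribution per 7.2 | Yes |
| Serious, SBRT alone | 7.3.2 (progression or complication reported as follow-up); 7.2 (late serious events) | Yes |
| Clinically significant laboratory abnormality, any cause | 7.4 | Yes |
| Non-serious, not a laboratory abnormality, SBRT alone | Table 6 says yes; 7.6 leaves it out | Conflict |

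Only the last row is exposed. Table 6 does not settle it, because its footnote sends the reader back to 7.6.

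**2. When does the visit fall relative to SBRT?**

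Inputs: 21-day cycles (Section 10); Off Treatment Visit 28 ± 7 days after the last dose (Table 6); SBRT starting on day 2 and lasting 5 to 15 days (Section 5.1). Assumptions: doses on schedule, and three months taken as 91 days.

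- SBRT ends between day 2 + 5 − 1 = 6 and day 2 + 15 − 1 = 16.
- Three months after SBRT falls between day 6 + 91 = 97 and day 16 + 91 = 107.
- After k doses the nominal visit is on day 1 + 21(k − 1) + 28.

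| Doses k | Nominal visit (± 7 days) | Days from nominal visit to three months after SBRT |
|---|---|---|
| 1 | 29 (22–36) | 68 to 78 |
| 2 | 50 (43–57) | 47 to 57 |
| 3 | 71 (64–78) | 26 to 36 |
| 4 | 92 (85–99) | 5 to 15 |
| 5 | 113 (106–120) | none (visit is 6 to 16 days later) |
| 6 | 134 (127–141) | none, even at the earliest visit |

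The last column is (97 to 107) minus the nominal day. After 1 to 4 doses the nominal visit comes before the three-month point; from 5 doses it comes after. With 5 doses, the earliest permitted visit (day 106) can still precede the latest three-month point (day 107) by one day.

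These days mark the period in which Section 5.1.2.1 looks for toxicity. They do not measure how long an open event lasts, and the documents give no durations. SBRT given later for oligoprogression (Section 5.3.2) has its own timing, which this table does not cover.

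**The case against.** The strongest reply is that this is a wording slip with little effect. Table 6 requires follow-up for everyone, and its pointer to 7.6 is only for details. Subjects who stop because of toxicity, the likeliest early stoppers with liver injury, have an intensified schedule in the same table. Laboratory follow-up in 7.4 has no attribution limit and covers much of non-classic radiation-induced liver disease, which Section 7.1.1.2 defines through enzymes and liver function. Serious events are protected by 7.2 and 7.3.2. Section 5.1.2.1 itself expects overlapping hepatic toxicity, so many hepatic events would be called possibly related to both components. Section 7.6 also asks for CRF data to be updated with new information.

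Most of this stands, and it limits the consequence to non-serious, SBRT-only events that are not laboratory abnormalities. It does not remove the conflict: 7.6 uses an exclusive word, Table 6 defers to it, and a site cannot tell which governs.

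A reader might infer three stronger things that the documents do not support:

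- **That SBRT toxicity is dropped and its grade and outcome are reported wrongly.** The event and its grade up to the visit are already recorded. What may be missing is the later course, so the record may be incomplete.
- **That SBRT toxicity will look shorter and milder than pembrolizumab toxicity.** Section 13.6.1 plans no analysis of duration or final outcome and no comparison of the two components.
- **That some 10 weeks of follow-up are lost in about a quarter of patients.** In Section 7.1.1.2 the period of two weeks to three months belongs to classic liver disease (under 5%). The figure of about 25% belongs to the non-classic form, defined within 12 weeks of starting therapy, or to about day 1 + 84 = 85. Both are onset periods, which say nothing about events already open. Multiplying 25% by 22 (5.5) or by the 27 who may be accrued (6.75) counts patients with an event. It does not count those whose event is open, non-serious and attributed to SBRT alone.

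**Conclusion.** The point holds as an inconsistency with a limited consequence for the safety data. Taken literally, 7.6 allows a non-serious adverse event attributed to SBRT alone and open at the Off Treatment Visit to go unfollowed, contrary to Table 6 and to the two-component wording of 7.2. If such an event worsens later, its worst grade in the Section 13.6.1 table may be too low and its outcome may be missing.

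For first-course SBRT this mainly concerns patients who stop after about 1 to 4 doses (nominal visit day 29 to 92, against day 97 to 107). Any such patient among the first 10 could bear on the Section 5.1.2.1 decision, though the laboratory and serious-event provisions narrow that route. The number affected cannot be computed: it could be zero, and the documents give no early-stopping rate or event durations from which to bound it usefully.

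This rests on reading *study drug* as pembrolizumab, on on-schedule dosing, and on three months as 91 days. The primary endpoint, sample size and error rates are not affected.

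**What to change.** Reconcile Section 7.6 with Table 6, Section 7.2 and Section 7.3.1 so that the attribution wording after the Off Treatment Visit covers both study treatments. Section 7.2 already has suitable wording in naming pembrolizumab or SBRT. State that the worst grade and outcome of events open at the visit are updated on the CRF at the contacts that Table 6 already schedules.

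The change is one phrase in 7.6 plus the cross-check, and it needs no new visits. The cost is a few more adverse event updates. Appendix 5 lists a three-monthly Short Follow-up Form, but the documents do not show its contents, so check whether it has room for these fields.
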